8.3. Examination findings

8.3.1. Patients Background

- Clinical diagnosis

Primary and metastatic lesion sites, etc.

- Clinical staging

Staging is determined in accordance with "UICC-TNM 7th Edition," and tumors will be classified according to the main histological type in each primary onset organ.

- The following details will be collected regarding the time of the initial histological diagnosis

(month and year), histological diagnosis, and the presence or absence of pretreatment.

- Presence or absence of surgery, indicated site, surgical procedure, date of surgery and results (e.g., R0)
- Presence or absence of adjuvant chemotherapy, treatment details, implementation period, and reason for termination
- Presence or absence of chemotherapy, treatment details, implementation period, and reason for termination
- Presence or absence of chemotherapy, site, implementation period, and radiation dose
- Presence or absence of other treatments, treatment details, and the implementation period

8.3.2. Height and weight measurements and vital signs

The subject's vital signs (i.e., blood pressure, heart rate, and body temperature) as well as body weight will be measured. Vital signs are to be measured at each examination with the subject in the same position each time.

8.3.3. ECOG Performance Status

The ECOG PS will be measured (refer to appendix 1).

8.3.4. Adverse events (subjective and objective symptoms)/combination therapy

During the period from the start of treatment until 30 days after completion of the treatment protocol, adverse events (subjective and objective symptoms) are to be monitored and recorded. Refer to section 11 on the reporting of adverse events for details regarding the handling of adverse events.

8.4. Laboratory tests

8.4.1. Blood tests/biochemical tests/blood coagulation tests/urine analysis/thyroid function tests

Blood tests/biochemical tests/blood coagulation tests/urine analysis/thyroid function tests
The items listed in Table 9 will be tested in accordance with the time indicated in the schedule presented in Table 10, and when deemed clinically necessary. If needed, the evaluation of clinically significant laboratory tests will be repeated until the test values return to baseline values, until clinically stable, or until a different treatment is initiated.

8.4.2. Tumor markers

The test items listed in Table 8.1 are to be measured in accordance with the time indicated

in the schedule presented in Table 8.2.

8.4.3. Pregnancy tests

In the case of a female subject capable of childbearing, confirmation that the subject is not pregnant will be obtained by urine test <14 days before enrollment in the trial. If pregnancy is suspected in the urine test, the pregnancy will be determined by a blood test. Female subjects deemed incapable of childbearing include those who have experienced menopause (the absence of menstrual periods for >1 year), and those who have undergone tube ligation or hysterectomy, the details of which are to be noted in the source document of the subject.

8.4.4. Infection tests

Anti-HIV antibodies, HBsAg, anti-HCV, HBs and HBc antibodies are to be measured before enrollment. Furthermore, in the event that results are available for tests conducted <12 months before enrollment, these results may be used instead.

HBV-DNA quantification is measured only when either HBs or HBc antibody is possible.

8.4.5. Twelve-lead ECG at rest

For the 12-lead ECG, data recording will be initiated after confirming that the subject is resting in the dorsal position. A physician suited to the ECG evaluation will evaluate the QT interval, as well as qualitative abnormalities in the ST segment form, the T-wave form, and the presence or absence of a U-wave.

8.5. Biomarkers

Biomarkers of tumor tissues of biopsies or past surgical specimens of patients agreed with “elucidation of immune status and clinical significance in patients with solid tumor including gastrointestinal cancer (Research Project Number: 2015-048)” consider. Details are described in the plan of the accompanying research.

8.6. Tumor evaluation

For all patients, tumor evaluations will be conducted using the irRECIST and RECIST guidelines version 1.1. Tumor evaluations of the chest, abdomen, and pelvis (when deemed clinically necessary) will be conducted at each time point listed below until an exacerbation is confirmed. Thoracoabdominal and pelvic contrast-enhanced CT or MRI will be performed (if the subject is allergic to the contrast medium, plain scans are permitted).

- Less than 21 days before enrollment in this trial

Evaluations will be performed in weeks 6, 12, 18, and 24 after the beginning of treatment (followed by every 9 weeks until week 42, then every 12 weeks thereafter).

- When treatment is terminated for reasons other than an exacerbation of the underlying disease on imaging, an evaluation will be performed within 2 weeks of dosing completion. Furthermore, tumor evaluations are to be conducted in accordance with the schedule until an exacerbation of the underlying disease is confirmed, or until commencement of a new anticancer treatment.

The principal investigator and radiologist will conduct tumor evaluations in accordance with the irRECIST and RECIST guidelines version 1.1 (refer to appendices 2 and 3). The decision to continue the investigational drugs will be determined on the basis of these evaluations, including the effects on target and nontarget lesions and the appearance of new lesions. When disease progression is first observed on imaging in clinically stable patients according to irRECIST, participating medical institutions will conduct repeat scans 4 weeks after the initial identification of disease progression via an image evaluation to determine disease progression. Administration of the investigational drug can continue until the repeat scan is conducted (refer to Table 8.6). The criteria for clinical stability are listed below.

- Absence of clinical signs and symptoms indicating disease progression.
- No worsening of ECOG PS.
- No sudden disease progression observed
- Absence of tumor enlargement in the main anatomical site requiring new emergency medical intervention (e.g., spinal cord compression).

Furthermore, in the present trial, a maximum of 5 lesions can be included as target lesions, with a maximum of two lesions per organ.

Table 8.6: Imaging and investigational drug dosing after disease progression is first observed on imaging

	Clinically stable		Clinically unstable	
	Imaging	Investigational drug dosing	Imaging	Investigational drug dosing
Disease progression is first determined	To confirm disease progression, repeat the test after 4	Investigational drug dosing can be continued at the	If possible, repeat the test after 4 weeks to confirm	Interruption of dosing

by imaging	weeks	discretion of the attending physician until disease progression is confirmed by retesting at the participating medical institution	disease progression	
Disease progression is determined by repeat imaging	Additional imaging is not necessary	Terminate dosing of the investigational drug (exceptions can be permitted upon deliberation with the trial coordinating committee)	Additional imaging is not necessary	Not applicable
SD, PR, or SD is determined by repeat imaging	Continue the prescribed routine imaging every 6 weeks	Continue the investigational drug at the discretion of the attending physician	Continue the prescribed routine imaging every 6 weeks	When the subject's condition improves, or when the subject is clinically stable, dosing of the investigational drug can resume at the discretion of the attending physician

8.7. Follow-up

Outcome investigations will be performed after termination of the treatment protocol until the subject dies, or up to 2 year after the day that the last subject enrolled in the present trial. Even when direct follow-up is not possible (e.g., because of hospital transfer), the

hospital where the subject was transferred will be contacted to verify the outcomes as far as possible. The results of such contact are to be noted in the subject's source documents.

9. DATA COLLECTION

9.1. Handling and Retention of CRF Data

Data will be managed, and CRF data will be managed and retained by the Data Management Office, Clinical Research Support Unit, and National Cancer Center Hospital East. A data management plan will be prepared. In the plan, access restriction such as inputting in and browsing the database will be set, and records will be properly controlled and kept.

9.2. Identification of Source Documents

Source documents in this study will be as follows:

- Medical records
- Informed consent form
- Investigational drug management table
- Laboratory test data
- Diagnostic imaging films, etc.

10. REPORTING OF ADVERSE EVENTS

10.1. Evaluation of AEs

10.1.1. Definition of AE

An adverse event (AE) is any unfavorable and unintended sign (including an abnormal laboratory value), symptom, or disease occurred in a patient administered the investigational drug, whether or not considered related to the investigational drug.

When \geq Grade 1 subjective symptom or objective finding has been observed since before treatment initiation (at baseline evaluation), it will be handled as an AE only when the grade of the concerned AE worsened from the baseline value.

10.1.2. Method for Recording AEs

When grading an AE, the closest definition should be selected among the definitions of Grades 0 to 5.

When a sign (including an abnormal laboratory value) or symptom is included in a diagnosis, the diagnostic term based on the CTCAE should be entered in the CRF to the extent possible instead of individual signs or symptoms.

Abnormalities of laboratory values or vital sign alone should be reported as AEs only when the investigator determined that they fall into any of the following cases:

- (1) Where a clinical sign or symptom is induced;
- (2) Where it is judged to be clinically important;
- (3) Where requiring treatment;
- (4) Where requiring an additional test (excluding a retest only); or
- (5) Where requiring treatment discontinuation or dose reduction for the investigational drug.

10.1.3. Items to Be Recorded for AEs

For AEs occurred, the following information should be reported in the CRF:

- (1) AE term;
- (2) Severity (CTCAE Grade 0 to 5 and serious/non-serious);
- (3) Causal relationship with the each drug;
- (4) Date of onset, date of outcome and outcome; and
- (5) Presence or absence of therapeutic action.

10.1.4. Assessment of the Causal Relationship

The causal relationship with the each investigational drug should be assessed on the following two categories:

“Definite,” “probable,” “p

Possible” or “unassessable” → “The causal relationship cannot be ruled out.”

“Unlikely” or “not related” → “The causal relationship can be ruled out.”

Table 10.1.4 Classification of causal relationship

Classification	Definition
Definite (certain)	The causal relationship with the protocol treatment is plausible and cannot be explained based on the progression of the primary disease, complications, other drugs/treatments, etc.
Probable (likely)	The causal relationship with the protocol treatment is reasonable and is unlikely to be due to the progression of the primary disease, complications, other drugs/treatments, etc.
possible	The causal relationship with the protocol treatment is reasonable and can be explained based on the progression of the primary disease, complications, other drugs/treatments, etc.
unlikely	The causal relationship with the protocol treatment is improbable and can be explained based on the progression of the primary disease, complications, other drugs/treatments, etc.
not related (unrelated)	There is no causal relationship with the protocol treatment, and it can be clearly explained based on the progression of the primary disease, complications, other drugs/treatments, etc.
unassessable (conditional)	An AE on which data to be assessed are insufficient, for which more detailed data are necessary (conditional), or which is difficult to assess.

10.1.5. Follow-up of the Clinical Course at the Onset of AEs

When an AE occurred, the investigator should immediately take an appropriate therapeutic action.

A symptom (laboratory value) should be followed up until resolution or remission is confirmed even after the AE evaluation period is ended (see the Section 10.1.6). However, the follow-up of an AE may be terminated if falling into at least any one of the following cases:

* In the case of terminating the follow-up of an AE:

- 1) Where it is not an SAE, is assessed that the causal relationship can be ruled out, and occurred at least 30 days after the day of the last dose;

- 2) Where the principal investigator determined that the symptom is stable and is not of a medically significant concern;
- 3) Where subsequent treatment was implemented so that the causal relationship with the investigational drug is unassessable;
- 4) Where the clinical course cannot be followed up due to reasons such as transfer to another hospital;
- 5) Where the patient refused to be followed up; or
- 6) Where the patient died.

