6.3.2. Criteria for Changes in Pembrolizumab therapy

6.3.2.1 Dose modification of Pembrolizumab

For AEs (whether serious or non-serious) related to pembrolizumab exposure, immunological factors may be involved. Such AEs may occur immediately after the start of investigational drug administration or several months after the last dose. For toxicity and

severe or life-threatening AEs related to pembrolizumab, pembrolizumab therapy should be interrupted or discontinued in accordance with Table 6.3.2.1.

Table 6.3.2.1. Dose modification of Pembrolizumab

General instructions:			
Immune-related AEs	Toxicity grade or conditions (CTCAEv4.0)	Action taken to pembrolizumab	Monitor and follow-up
Pneumonitis	Grade 2	Withhold	
 Monitor participants for signs and symptoms of pneumonitis Evaluate participants with suspected pneumonitis with radiographic imaging and initiate corticosteroid treatment Add prophylactic antibiotics for opportunistic infections
	Grade 3 or 4, or recurrent grade 2	Permanently discontinue	
Diarrhea / colitis	Grade 2 or 3	Withhold	
 Monitor participants for signs and symptoms of enterocolitis (i.e. diarrhea, abdominal pain, blood or mucus in stool with or without fever) and of bowel perforation (i.e. peritoneal signs and ileus). Participants with \geq Grade 2 diarrhea suspecting colitis should consider GI consultation and performing endoscopy to rule out colitis.
	Grade 4	Permanently discontinue	

			
 Participants with diarrhea/colitis should be advised to drink liberal quantities of clear fluids. If sufficient oral fluid intake is not feasible, fluid and electrolytes should be substituted via IV infusion.
AST / ALT elevation or Increased Bilirubin	Grade 2	Withhold	
 Monitor with liver function tests (consider weekly or more frequently until liver enzyme value returned to baseline or is stable)
	Grade 3 or 4	Permanently discontinue	
Type 1 diabetes mellitus (T1DM) or Hyperglycemia	Newly onset T1DM or Grade 3 or 4 hyperglycemia associated with evidence of β -cell failure	Withhold	
 Monitor participants for hyperglycemia or other signs and symptoms of diabetes.
Hypophysitis	Grade 2	Withhold	
 Monitor for signs and symptoms of hypophysitis (including hypopituitarism and adrenal insufficiency)
	Grade 3 or 4	Withhold or permanently discontinue ¹	

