For the time period beginning at treatment through 90 days following cessation of treatment, or 30 days following cessation of treatment if the participant initiates new anticancer therapy, whichever is earlier, any serious adverse event, or follow up to a serious adverse event, including death due to any cause whether or not related to the Provider product, must be reported within 24 hours to the Sponsor and within 2 working days of but not longer than three 3 calendar days of receipt of the information to Merck Global Safety.

Additionally, any serious adverse event, considered by an investigator who is a qualified physician to be related to Provider product that is brought to the attention of the investigator at any time following consent through the end of the specified safety follow-up period specified in the paragraph above, or at any time outside of the time period specified in the previous paragraph also must be reported immediately to Merck Global Safety.

All participants with serious adverse events must be followed up for outcome.

SAE reports and any other relevant safety information are to be forwarded to the Merck Global Safety [contact]

10.2.2. . Reporting Obligation of the Investigator and Reporting Procedures

1) Report to the head of the study site and the coordinating committee

① Initial report

When an SAE (see the Section “10.2”) occurred, the investigator should immediately take an appropriate action. The subinvestigators should promptly report it to the principal investigator.

The investigator should report an SAE occurred in writing (e-mail* or fax) or orally (telephone) to the head of the study site and the coordinating committee within 24 hours after learning its onset. When the initial report is made without using the “SAE Report,” a report should be promptly made using the said form (e-mail or fax).

In addition, the details of the SAE should be reported in writing to the head of the study site and the coordinating committee within 2 business days after learning its onset.

* Reporting by e-mail is recommended.

② Additional report

The principal investigator should follow up the SAE (see the Section “10.2”). Additional information should be recorded in the “SAE Report” (additional report) and promptly sent to the head of the study site and the coordinating committee within 2 days after learning its onset.

Contact information of the coordinating committee: Clinical Study Coordinating Secretariat

E-mail: [contact]

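### Section 10.1.5 lets follow-up of an SAE end once later treatment has made causality unassessable, although 10.2.1 requires every SAE to be followed for outcome

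*Combined protocol and SAP*

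**What the plan says.** Section 10.1.5 starts from a strict default: a symptom or laboratory value "should be followed up until resolution or remission is confirmed even after the AE evaluation period is ended". It then relaxes this: "the follow-up of an AE may be terminated if falling into at least any one of the following cases". Six cases follow.

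- Case 1 is restricted by seriousness, causality and timing. It begins "Where it is not an SAE, is assessed that the causal relationship can be ruled out" and goes on to require onset at least 30 days after the last dose.
- Case 2: "Where the principal investigator determined that the symptom is stable and is not of a medically significant concern".
- Case 3: "Where subsequent treatment was implemented so that the causal relationship with the investigational drug is unassessable".
- Cases 4 to 6 cover patients whose course cannot be followed (for example after transfer), patients who refuse, and patients who have died.

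Section 10.2.1 closes its SAE reporting rules with "All participants with serious adverse events must be followed up for outcome". Section 10.2.2 separately tells the principal investigator to follow up the SAE. Neither passage refers to the cases in 10.1.5.

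Section 10.1.4 places unassessable causality in the group where a causal relationship cannot be ruled out, together with definite, probable and possible.

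**The concern.** One section permits what the other forbids. Case 1 shows that the drafters excluded SAEs where they meant to. The absence of that exclusion in cases 2 and 3 therefore reads as including them. Section 10.1.3 requires outcome and date of outcome on the CRF for every AE, so an SAE closed under case 3 could be left without a required data item. Causality is a separate item in the same list, and difficulty in judging it is not in itself a reason to leave the outcome blank.

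Safety is a secondary objective of this 29-patient trial. What is at stake is whether the SAE listing shows how each non-fatal serious event ended. The point concerns events already open. It does not concern how long after treatment new events are collected.

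**Working it through.** No formula applies, and the plan gives no figure to reproduce. The check sets the sections side by side.

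1. **Does the term AE in 10.1.5 include SAEs?** Yes. Section 10.2.1 defines SAEs as those AEs of section 10.1 that meet further criteria.

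2. **Which cases can close an SAE?**

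| Case in 10.1.5 | Limited to non-serious events? | Set against 10.2.1 |
|---|---|---|
| 1. Not serious, causality ruled out, late onset | Yes | No conflict |
| 2. Stable and of no medically significant concern | No | Weak conflict |
| 3. Later treatment has made causality unassessable | No | Firm conflict |
| 4. Course cannot be followed | No | Practical limit |
| 5. Refusal | No | Practical limit |
| 6. Death | No | Death is itself an outcome |

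One case of six excludes SAEs, which leaves 6 − 1 = 5. Three of those (4 to 6) are largely unavoidable. The discretionary ones number 5 − 3 = 2, namely cases 2 and 3.

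3. **Case 2.** Two conditions must hold together, in the principal investigator's judgement: stability and no medically significant concern. Section 10.2.1 asks for follow-up to outcome and does not say to resolution. A stable state could be entered as that outcome, and the two rules would then be compatible. The gap is that 10.1.5 does not require the entry.

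4. **Case 3.** Two conditions must hold together here too: subsequent treatment has been given, and it has made causality unassessable. Neither tells anyone how the event ended, so the outcome can remain open. Under 10.1.4 the same event is still one whose relation to study drug cannot be ruled out.

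5. **Reach into the analyses.** Section 11.2.5 defines AE incidence by worst grade during all cycles, and 12.6 tabulates frequencies in the safety population. No analysis of AE outcome is specified. Under 10.1.6 the AE evaluation period ends before subsequent treatment starts, so case 3 acts only after that period has closed. Date and cause of death are collected through the outcome investigation in Table 8.1 and section 8.7. The exposed data are therefore the outcomes of non-fatal SAEs still open when later treatment begins.

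**The case against.** The strongest reply is that 10.1.5 grants a permission and 10.2.1 imposes a duty. A site that follows every SAE to outcome satisfies both, and a specific SAE rule might be read as overriding a general AE rule. The first part stands: a reader might infer that following 10.1.5 necessarily breaches 10.2.1, and it does not. Only using the permission for an SAE does. The second part is an interpretation that the documents do not state, and the explicit exclusion in case 1 tells against it.

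Other stronger readings are tempting but unsupported:

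- *That starting a new therapy, or calling an event stable, is enough to stop.* Each case has a second condition, set out above.
- *That an immune-related SAE beginning near the last dose could be dropped as soon as new therapy starts, before a corticosteroid taper of 4 or more weeks is finished.* An event that began before the new drug does not become unassessable merely because that drug is started. The taper in 6.3.2.2 follows recovery to Grade 1, so its length is not a minimum duration of the event. Note f to Table 8.2 also calls for safety tests, or a telephone check, before new therapy.
- *That 10.1.4 and 10.1.5 use unassessable in contradictory senses.* The definition in Table 10.1.4 offers alternatives, "for which more detailed data are necessary (conditional), or which is difficult to assess", and confounding by a later drug fits the last of them. The term can stay. What remains is that case 3 can end follow-up of an event still counted as possibly related.
- *That a particular number of outcomes, or a selective loss, can be predicted.* The documents give neither an SAE rate nor the share of patients who would meet case 3.

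**Conclusion.** The conflict is real and narrow. It is firm for case 3 and weak for case 2. A site that closes an SAE under case 3 breaches 10.2.1 and may leave a non-fatal outcome unrecorded. The loss is possible rather than demonstrated, and no count can be attached to it. ORR, the two-stage design, its error rates and the planned AE incidence tables are untouched.

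The conclusion rests on two readings: that an unqualified reference to an AE includes serious ones, and that no other text ranks the two sections. Both follow from the documents as supplied. This is a modest safety-data correction, worth making because it is cheap and because 10.1.3 already requires the outcome item.

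**What to change.** Reconcile the sections within 10.1.5:

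- Limit case 3 to non-serious AEs, as case 1 already is.
- Add to case 2 that, for an SAE, the stable state is recorded as the outcome before follow-up ends.
- Leave cases 4 to 6 as they are. Section 10.1.4 needs no change.

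The cost is one or two sentences, plus a few extra record or telephone checks among 29 patients who are already followed for survival under 8.7. The change affects data collection only.
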